9.6 Timepoints

Screening – trial enrolment time window

Enrolment should take place no longer than 120 days following the date of screening appointment. If more than 120 days elapse, the screening visit should be repeated in full prior to enrolment in order to minimise the risk to participants of any new unidentified health problems having arisen during that period.

Vaccination of first volunteer – subsequent vaccination time window

The first volunteer, who will be allocated to the Starter Group, will be vaccinated with MVA85A by the aerosol inhaled route at least 48 hours before any subsequent volunteers in this group. After safety review, the first volunteer in Group A will be vaccinated at least 48 hours prior to further enrolment.

Vaccination – bronchoscopy time window

According to our clinical research (and in line with pre-clinical findings), the peak effector T cell response detected from PBMC in venous blood samples is around seven days after vaccination with MVA85A. In our previous trial of aerosolised MVA85A, high frequencies of Ag85A-specific cytokines were detected in BAL samples at one week post-vaccination, therefore bronchoscopy will be performed at seven days to match that trial.

Follow up period

The follow up period will be six months in accordance with findings from previous trials in which adequate safety data and reliable markers of immunogenicity have been obtained in this time interval.

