4.2 Schedule of visits and procedures

Table 1. Schedule of trial procedures

Attendance number	1	2	3	4	5	6	7	8
Timeline (days)*	S	0	2	7	14	28	84	168 ^T
Timeline (weeks)*	S	0		1	2	4	12	24
Time windows (days)			±1	+4, -2	±4	±7	±14	±21
Inclusion/exclusion criteria	X							
Review contra-indications	X	X		X				
Informed consent	X							
Medical history	X	(X)	(X)	(X)	(X)	(X)	(X)	(X)
Physical examination	X			X				
Vital signs	X	X	X	X	X	X	X	
Urinalysis	X							
CT chest	X					X		
PFTs	X	X	X	X	X			
β-HCG urine test	X	X		X				
Vaccinations		X						
Bronchoscopy				X				
Local & systemic events/reactions		X	X	X	X	X	X	X
Ediary setup		X						
Ediary final review					X			
Biochemistry (4mL)**	X		X	X		X		
Haematology (2mL)	X			X		X		
Coagulation (4mL)	X							
HBV, HCV, HIV (10mL)	X							
HLA typing (4mL)		X						
Exploratory immunology incl ELISpot (16-60mL***)	X	X	X	X	X	X	X	
Blood vol (mL)	30	64	20	56	60	66	60	
Cumulative blood vol (mL)****	30	94	114	170	230	296	356	

S Screening

X Event scheduled to occur

(X) If considered necessary, emphasising any complaint or change in medications

T Telephone call. Final visit is deemed to be at D84 with follow up phone call at D168

* Timeline is approximate only, as exact timings (± windows periods) of visits relate to the actual (not intended) date of the previous visit

** U&Es, LFTs (except day 2 when CRP only;)

*** 60ml at all visits except screening (10ml, T spot), visit 3 (16ml, no ELISpot) and visit 4 (50ml)

**** Blood volumes stated for Oxford. The exact volumes of blood taken will depend on the local site – cumulative blood volumes for volunteers outside Oxford may be slightly lower or higher than those of Oxford volunteers, due to the use of different volume vacutainers for biochemistry, haematology and serology samples as per local Trust standard procedures

Grey Highlights vaccination day

Blue Highlights bronchoscopy day

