9.4 Screening and Eligibility Assessment

Once the volunteer has given their consent to undergo screening, a baseline medical history (including concomitant medication) and physical examination will be performed by a GCP trained doctor. Inclusion and exclusion criteria will be checked using a tabulated format. Demographic and occupational data relating to risk of prior *M.tb* exposure will be collected. Vital signs will be checked and bloods taken including FBC, clotting profile, U&Es, CRP, LFTs, HIV antibodies, HBsAg, HCV antibodies and IGRA. Volunteers will be counselled by one of the Investigators for HIV, Hepatitis B and Hepatitis C testing. Urine will be tested for the presence of clinically significant proteinuria, glycosuria or haematuria. A pregnancy test will be performed for female volunteers. Volunteers will then be scheduled to re-attend for a CT thorax provided no exclusion criteria have been met.

Laboratory parameters for inclusion/exclusion in the trial will be considered on an individual basis, with Investigator discretion for interpretation of results and the need for repeated tests. In general, volunteers will be excluded if a result at screening constitutes what would qualify as a grade 1 (or higher) laboratory AE, according to the site-specific laboratory AE tables, filed in the TMF (Oxford), or Site Master File (Birmingham and London).

The total duration of the screening visit will be around 2 hours.

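### No safety bloods are scheduled on day 0, so the only planned pre-vaccination biochemistry and haematology may be up to 120 days old at vaccination

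*Combined protocol and SAP*

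**What the plan says.** Table 1 in section 4.2 marks biochemistry (4 mL) at screening, day 2, day 7 and day 28, and haematology (2 mL) at screening, day 7 and day 28. On day 0 it marks only HLA typing and exploratory immunology. Vital signs and pulmonary function tests are repeated on day 0.

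Section 9.6 governs the gap between screening and entry: "Enrolment should take place no longer than 120 days following the date of screening appointment". Beyond that, "If more than 120 days elapse, the screening visit should be repeated in full prior to enrolment". Section 9.5 places group allocation and vaccination at the same day 0 visit.

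On CRP, the footnote to the biochemistry row of Table 1 reads "U&Es, LFTs (except day 2 when CRP only". Section 9.4 describes screening differently: "Vital signs will be checked and bloods taken including FBC, clotting profile, U&Es, CRP, LFTs".

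Section 11.2 includes abnormal laboratory findings in the definition of an adverse event. Section 11.8 grades laboratory adverse events against site-specific tables. Section 12 records that the comparator arm has been removed. No analysis of laboratory change from baseline is defined.

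**The concern.** The primary objective is safety, assessed through adverse events. Table 5 (section 11.5) bases causality on timing relative to vaccination, on whether clinical state, environment or other interventions could explain the event, and on the known response pattern. The first two criteria are easier to apply to a laboratory result when there is a value from just before vaccination. Without one, an abnormality first seen on day 2, 7 or 28 could have arisen at any time since screening.

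A concurrent control group would give some protection, because drift unrelated to vaccine would appear in both arms. This trial has 6 to 9 volunteers and no such group, so attribution depends on each volunteer's own sequence of values.

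Two features sharpen the point. CRP is the only biochemistry result on day 2, close to the 48-hour safety review that must precede further vaccinations (section 6.2). Also, section 9.2 keeps volunteers eligible if they do not want chemoprophylaxis delayed, so treatment could change between screening and day 0 with no fresh laboratory value to show its effect.

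**Working it through.** **Step 1. Is the day 0 gap real, or a damaged table?** The per-visit volumes in Table 1 can be rebuilt from the tubes marked at each visit. The immunology volumes come from the footnote: "60ml at all visits except screening (10ml, T spot), visit 3 (16ml, no ELISpot) and visit 4 (50ml".

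| Visit | Tubes (mL) | Sum | Stated |
|---|---|---|---|
| Screening | biochemistry 4 + haematology 2 + coagulation 4 + serology 10 + immunology 10 | 30 | 30 |
| Day 0 | HLA 4 + immunology 60 | 64 | 64 |
| Day 2 | biochemistry 4 + immunology 16 | 20 | 20 |
| Day 7 | biochemistry 4 + haematology 2 + immunology 50 | 56 | 56 |
| Day 14 | immunology 60 | 60 | 60 |
| Day 28 | biochemistry 4 + haematology 2 + immunology 60 | 66 | 66 |
| Day 84 | immunology 60 | 60 | 60 |
| Total | | 356 | 356 |

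Every figure reproduces. The day 0 volume is fully used by HLA typing and immunology, so the absence of safety bloods is the plan's intention.

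**Step 2. How old can the screening value be?** Enrolment is taken as day 0, because allocation and vaccination share that visit. Maximum age = 120 + days from vaccination to the draw.

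- Nominal days: 120 + 2 = 122; 120 + 7 = 127; 120 + 28 = 148.
- With each visit's own late window (+1, +4, +7): 123, 131 and 155.
- With windows accumulating from the previous actual visit, as the Table 1 timeline note provides: 120 + 2 + 1 = 123; 120 + 7 + 1 + 4 = 132; 120 + 28 + 1 + 4 + 4 + 7 = 164. The second 4 in the last sum is the day 14 window.

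**Step 3. What would a day 0 sample cost in blood?** Day 0: 64 + 4 + 2 = 70 mL. Total: 356 + 6 = 362 mL, an increase of 6/356 = 1.7%.

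**Step 4. CRP, passages side by side.** Table 1 schedules biochemistry four times, and its footnote names CRP for day 2 only. Section 9.4 adds CRP at screening. Read together, CRP is named at two times: screening and day 2. Section 9.4 concerns screening alone and does not settle days 7 and 28, so it remains unclear whether CRP is measured then.

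**The case against.** The case for leaving the plan alone has several good parts.

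- **Grading does not use baseline.** Laboratory adverse events are graded against site tables, and no change-from-baseline analysis is specified. A reader might infer that the planned analysis compares results with a stale baseline; the documents do not say so. What is affected is causality judgement and the description of shifts.
- **Screening filters abnormal values.** Section 9.4 in general excludes anyone with a grade 1 or higher screening result, so a later graded abnormality is usually new since screening. This stands, but new since screening is not the same as new since vaccination.
- **There are clinical checks on day 0.** New symptoms are assessed, eligibility is reviewed, and section 9.8 postpones vaccination for fever, recent upper respiratory infection, or moderate or severe acute illness. These reduce the chance of an intercurrent cause, but they would not detect a laboratory abnormality without symptoms.
- **Later values help.** U&Es, LFTs and haematology are drawn on both day 7 and day 28, so resolution can be observed, and clinically significant results may be repeated. This informs the course of an abnormality, not its onset.

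A reader might also infer that day 2 CRP has no baseline at all. Section 9.4 takes CRP at screening, so it has one, though possibly an old one. Nor does it follow that post-vaccination abnormalities cannot be attributed: timing, response pattern and clinical context remain available.

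**Conclusion.** The point holds as a cheap improvement to the design, not as an error in a stated analysis. No biochemistry or haematology is scheduled on day 0, and the only planned pre-vaccination values may be up to 120 days old at vaccination. In a small trial without a comparator, this makes a laboratory abnormality first seen on day 2, 7 or 28 harder to place before or after vaccination, and so weakens the causality assessment of laboratory adverse events.

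The size is limited. The ages in the working are ceilings; the documents do not give the typical gap from screening to vaccination. Expressing 120 days as a share of the interval (120/122 is 98% for day 2) gives a calendar ratio, which should not be read as a probability of misattribution. The conclusion assumes that enrolment coincides with day 0 and that no unscheduled repeat bloods are taken in between.

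The CRP difference between the Table 1 footnote and section 9.4 is a minor inconsistency.

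**What to change.** Add biochemistry including CRP (4 mL) and haematology (2 mL) to the existing day 0 draw, taken before vaccination. State in section 11 or 12 that the day 0 result is the reference value when post-vaccination laboratory findings are described and attributed. Update the volumes in Table 1 (day 0 from 64 to 70 mL, cumulative from 356 to 362 mL) and in section 6.3.

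The cost is 6 mL more blood per volunteer from a venepuncture already planned, and routine assays for 6 to 9 people. No extra visit or needle is needed.

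Separately, reconcile the Table 1 footnote with section 9.4, and make the footnote state at which biochemistry visits CRP is measured. This is a wording change.

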9.7 Sample handling

Details regarding samples, volume and frequency of sampling are listed in the Schedule of Trial Procedures (section 4.2). Blood samples will be processed according to local laboratory standard operating procedures. All samples will be in anonymised form at the CCVTM; samples at Birmingham and London sites may contain patient numbers and details as per NHS procedures.

Volunteers will be informed that there may be leftover samples of their blood. With the volunteers' informed consent, any leftover cells and serum, plasma or BAL samples will be frozen for future analysis of *M.tb* and/or vaccine-related responses. This may include human DNA and RNA analysis to search for correlates of vaccine immunogenicity and efficacy. Samples may be shipped to other parties involved in our research in anonymised form for immunological analysis. Volunteers will be able to decide if they will permit such future use of any leftover samples. If they elect not to permit this, all of those leftover samples will be discarded after the required period of storage to meet GCP and regulatory requirements.

9.8 Vaccination Postponement Criteria

Vaccination will not proceed on the scheduled day in any of the following situations:

- The volunteer has a current or recent upper respiratory tract infection, unless they have been symptom-free for at least one week
- The volunteer has a positive pregnancy test
- The volunteer has a temperature > 37.5°C
- The Investigator judges the volunteer to have an acute moderate or severe illness (whether febrile or not)
- The volunteer has received a live non-trial vaccine within the preceding 28 days
- The Investigator has any other concern that vaccination may not be in the volunteer's best interests

In this case the volunteer may be vaccinated at a later date or withdrawn from the trial at the discretion of the Investigator.

9.9 Bronchoscopy Postponement criteria

Bronchoscopy will not proceed on the scheduled day in any of the following situations:

- The volunteer has a temperature > 37.5°C
- The volunteer has a positive pregnancy test
- The Investigator judges the volunteer to have an acute moderate or severe illness (whether febrile or not)
- The Investigator has any other concern that bronchoscopy may not be in the volunteer's best interests

In the event of postponement the bronchoscopy will be rescheduled when possible up to a 3 week window.

9.10 Discontinuation / Withdrawal Criteria

Every reasonable effort will be made to maintain protocol compliance and participation in the trial.

In accordance with the principles of the current revision of the Declaration of Helsinki and any other applicable regulations, a volunteer has the right to withdraw from the study at any time and for any reason, and is not obliged to give his or her reasons for doing so. The Investigator may withdraw the volunteer at any time in the interests of the volunteer's health and well-being (including on the advice of the LSC). In addition the volunteer may withdraw/be withdrawn for any of the following reasons:

- Administrative decision by the Investigator
- Ineligibility (either arising during the trial or retrospectively, having been overlooked at screening)
- Significant protocol deviation
- Volunteer non-compliance with trial requirements (failure to attend two or more follow-up visits)
- Any AE which requires discontinuation of trial involvement or results in inability to comply with trial procedures
- Confirmed pregnancy during the trial

Any volunteer who becomes pregnant during the trial will be followed up as per the protocol and until the end of the pregnancy. We will not routinely perform venepuncture in a pregnant volunteer.

The reason for withdrawal will be recorded in the CRF. Volunteers withdrawn from the trial may be replaced on the decision of the Investigator. If the volunteer is withdrawn due to an AE, the Investigator will arrange for appropriate specialist management or follow up visits or telephone calls until the AE has resolved or stabilised. The regulatory authorities will be informed in a timely manner. The extent of follow up after premature discontinuation will be determined by the Investigator but will be at least for the whole trial period, and if pregnant, until pregnancy outcome.

If a volunteer withdraws from the trial, samples collected before their withdrawal from the trial will be used/stored unless the volunteer specifically requests otherwise. Long term safety data collection will continue as appropriate if a volunteer has received one or more vaccine doses.

9.11 Safety

Discontinuation of the trial

The trial will be discontinued in the event of any of the following:

- New scientific information is published to indicate that volunteers in the trial are being exposed to undue risks as a result of administration of the IMP, or as a result of the trial procedures or follow-up schedule.
- Serious concerns about the safety of the IMP arise as a result of one or more vaccine related SAE(s) occurring in the volunteers enrolled in this or any other ongoing trial of the MVA85A vaccine.
- For any other reason at the discretion of the Investigator.

9.12 End of Trial Definition

The trial will be completed when the last volunteer enrolled into the trial has completed the final follow up telephone call. An end of trial letter will be sent to each volunteer's GP and their TB clinician.

10 INVESTIGATIONAL MEDICINAL PRODUCT AND DEVICES

10.1 IMP Description

The MVA85A vaccine consists of the attenuated vaccinia virus MVA vector with a 1176 base-pair insert, which is almost the complete *M.tb* gene for Ag85A, with the tissue plasminogen activator (TPA) signal sequence preceding the N terminus and a monoclonal antibody tag (pk) at the C terminus. Expression of the antigen 85A DNA sequence is regulated by the vaccinia P7.5 early/late promoter. MVA85A is manufactured under Good Manufacturing Practice conditions by IDT Biologika GmbH (IDT), Germany.

MVA85A is supplied as a sterile liquid in glass vials. Each vial of lot 0050811 contains 400 µL of vaccine at a concentration of 8.4×10^8 pfu/mL in 10mM Tris buffer 140 mM NaCl; pH 7.7. The dose of MVA85A to be used in the starter group will be 1×10^7 pfu (120 µL of a 1:10 dilution, as per Vaccine Dilution SOP) diluted in saline and administered by aerosol inhalation. The dose of MVA85A to be used in Group A will be 5×10^7 pfu (60µl) diluted in saline for aerosol inhalation.

10.2 Storage of IMP

MVA85A will be shipped from IDT directly to the Clinical Biomanufacturing Facility (CBF) on dry ice and in the presence of a temperature logger. The vaccine will be certified and labelled for use in trial TB040 by a qualified person (QP) at the University of Oxford.

The vaccine will be stored at -80°C (nominal temperature) in a secure, temperature-monitored freezer at the Centre for Vaccinology and Tropical Medicine, University of Oxford, Churchill Hospital.

10.3 Dispensing and administration

All movements of vials of the trial vaccine between IDT and the University of Oxford and in or out of the locked freezer will be documented. Vaccine accountability, storage, shipment and handling will be in accordance with local SOPs and other relevant local forms.

On vaccination day, vaccines will be allowed to thaw to room temperature and will be administered within 1 hour. The vaccine will be administered by aerosol inhalation, according to the trial-specific SOP. Volunteers will stay in the unit for 60 minutes (± 10 minutes) after vaccination. During the administration of the vaccine, monitoring equipment, oxygen, medicines including bronchodilators and resuscitation equipment will be immediately available for the management of anaphylaxis and bronchospasm according to the site-specific SOP.

In order to minimise dissemination of the recombinant vectored vaccine virus into the environment, a number of measures will be instituted during and following vaccination:

- The dilution process will be carried out in a sealed vial in accordance with the vaccine dilution SOP.
- The aerosol inhaled vaccination will take place in a closed clinic room and not opened until 10 minutes after the end of nebulisation.
- During aerosol inhalation clinical staff will wear appropriate protective clothing as agreed with the GMSC.
- All disposable items including nebuliser parts, needles, vials, dressings, and protective clothing will be disposed of as GMO waste by autoclaving, in accordance with the current approved SOP and the contained use GMO regulations 2014.
- All hard surfaces within the clinic room where vaccination took place will be cleaned and disinfected in accordance with GMSC recommendations.
- Non-disposable parts of the MicroAIR NE-U22 nebuliser will be cleaned and disinfected in accordance with the device documentation and GMSC recommendations.

10.4 Saline

Sterile saline will be used for dilution of MVA85A (as needed, to achieve the correct dose). Once prepared, the vaccine will then be made up to 1ml with saline for administration via the MicroAIR NE-U22 nebuliser.

10.5 MicroAIR NE-U22

This is an approved electromedical device, CE0197, EAN code 40 15672 10142 1. Information about the specifications, usage, and maintenance of the nebuliser device can be found in the device documentation (65). This is the same device used in studies TB026 and TB035.

10.6 Sedative & anaesthetic agents for bronchoscopy

Fentanyl is a licensed opioid used routinely to provide analgesia and sedation during medical procedures. It will be stored, dispensed and administered in accordance with standard NHS procedures and the Summary of Product Characteristics (SmPC).

Midazolam is a licensed benzodiazepine used routinely to provide sedation and amnesia during medical procedures. It will be stored, dispensed and administered in accordance with standard NHS procedures and the SmPC.

Lignocaine is a licensed local anaesthetic used routinely during medical procedures. It will be stored, dispensed and administered in accordance with standard NHS procedures and the SmPC.

Other licensed drugs may be used during bronchoscopy at the discretion of the Investigators.

11 ASSESSMENT OF SAFETY

Safety will be assessed by the frequency, incidence and nature of adverse events and serious adverse events arising during the study.

11.1 Interim Safety Review

Prior to dose escalation of the vaccine, the clinical team and Chief Investigator will review the safety data and adverse events in volunteers before proceeding to the next vaccine dose. Interim safety data may also be made available to manufacturers (in coded format) as specified in the contract with the manufacturer(s).

11.2 Definitions

Adverse Event (AE)

An AE is any untoward medical occurrence in a volunteer, which may occur during or after administration of an Investigational Medicinal Product (IMP) and does not necessarily have a causal relationship with the intervention. An AE can therefore be any unfavourable and unintended sign (including an abnormal laboratory finding), symptom or disease temporally associated with the study intervention, whether or not considered related to the study intervention.

Each adverse event will be graded by the participant according to the table for grading severity of adverse events (see Section 11.7). Severity gradings may be reviewed and discussed with the participants at the clinic visits.

Adverse Reaction (AR)

An AR is any untoward or unintended response to an IMP. This means that a causal relationship between the IMP and an AE is at least a reasonable possibility, i.e., the relationship cannot be ruled out. All cases judged by the reporting medical Investigator as having a reasonable suspected causal relationship to an IMP (i.e. possibly, probably or definitely related to an IMP) will qualify as adverse reactions.

Unexpected Adverse Reaction

An adverse reaction, the nature or severity of which is not consistent with the applicable product information (e.g., IB for an unapproved IMP).

Serious Adverse Event (SAE)

An SAE is an AE that results in any of the following outcomes, whether or not considered related to the study intervention.

- Death.
- Life-threatening event (i.e., the volunteer was, in the view of the Investigator, at immediate risk of death from the event that occurred). This does not include an AE that, if it occurred in a more severe form, might have caused death.

- Persistent or significant disability or incapacity (i.e., substantial disruption of one's ability to carry out normal life functions).
- Hospitalisation or prolongation of existing hospitalisation, regardless of length of stay, even if it is a precautionary measure for continued observation. Hospitalisation (including inpatient or outpatient hospitalisation for an elective procedure) for a pre-existing condition that has not worsened unexpectedly does not constitute a serious AE.
- An important medical event (that may not cause death, be life threatening, or require hospitalisation) that may, based upon appropriate medical judgment, jeopardise the volunteer and/or require medical or surgical intervention to prevent one of the outcomes listed above. Examples of such medical events include allergic reaction requiring intensive treatment in an emergency room or clinic, blood dyscrasias, or convulsions that do not result in inpatient hospitalisation.
- Congenital anomaly or birth defect.

Serious Adverse Reaction (SAR)

An adverse event (expected or unexpected) that is both serious and, in the opinion of the reporting Investigator or Sponsors, believed to be possibly, probably or definitely due to an IMP or any other study treatments, based on the information provided.

Suspected Unexpected Serious Adverse Reaction (SUSAR)

A serious adverse reaction, the nature and severity of which is not consistent with the information about the medicinal product in question set out in the IB or SmPC.

NB: To avoid confusion or misunderstanding the following note of clarification is provided: "Severe" is often used to describe intensity of a specific event, which may be of relatively minor medical significance. "Seriousness" is the regulatory definition supplied above.

